3.5 VISIT SCHEDULE

The Week 12 visit for the pivotal studies NI-AC301 or NI-AC302 will serve as the Baseline Visit for this long term safety study. Subjects must have completed the full 12 weeks of treatment in one of the pivotal studies to enroll in the long term safety study. Subjects may enter the long term safety study up to 7 calendar days after their Week 12 visit in the pivotal study. Study visits will take place after the first four weeks then at Weeks 4, 12, 24, 36 and 40.

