### 4.4 Extent and Duration of Exposure

Summaries of the duration of exposure, days of exposure, and extent of exposure (calculated total grams) to study drug will be presented, overall and by whether previously randomized to SB204 (SB204 experienced) or randomized to Vehicle (SB204 naïve). This information plus study drug management details will be listed as well. All exposure endpoints will take into account whether the subject received SB204 in the previous study (NI-AC301 or NI-AC302).

Duration of exposure will be defined as:

Date of Last Drug Administration – Date of First Drug Administration + 1 day

Where date of first drug administration is the date of first treatment in the previous pivotal study for subjects randomized to SB204 in the previous study, and date of first dose in the LTS for subjects randomized to vehicle in the previous study.

Days of exposure will be defined as the total number of days that the subject reported taking study medication, and includes the days of exposure to SB204 in the previous study (NI-AC301 or NI-AC302) if applicable.

Extent of exposure will be based on the number of areas treated (face, upper back, and/or upper chest/shoulders, and any other areas reported) and the number of days with treatment. For subjects randomized to SB204 in the previous studies, drug was only applied to the face so for the days of exposure from the previous studies, it will be assumed that there is only one area of application, i.e. the face.

Each application is equal to 0.9 g. Extent of exposure is estimated as the sum of application areas (face only=1, face and chest=2, etc.) times the number of days of application to those areas times 0.9g. For example, a subject who applies 200 applications to the face only will have extent of exposure = 180g, while a subject who applies 100 applications to the face and 50 applications to the upper back will have extent of exposure = 135 g. The maximum extent of exposure would be: [0.9 grams x number of days on treatment in previous study] + [0.9 grams x 4 areas x number of LTS days on treatment]. Most subjects will have less exposure than this, so extent of exposure will be categorized logically depending on actual distribution of subjects. Initially, quartiles will considered.

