#### 4.5 Safety

#### 4.5.1 Adverse Events

All AEs that occur during the study or continue after enrollment into this study will be recorded and classified on the basis of Medical Dictionary for Regulatory Activities (MedDRA) terminology version 18.1. Adverse events ongoing at end of the pivotal study will be carried forward to this study, will not be considered treatment-emergent for this study, and will be summarized separately by SOC, PT, and relatedness. Treatment-emergent AEs (TEAEs) will be defined as AEs reported on or after the first day of enrollment in this long term safety study.

All information pertaining to an AE noted during the study will be listed by subject, detailing verbatim term given by the Investigator or designee, preferred term, system organ class (SOC), onset date, resolution date, severity, seriousness, action taken, outcome, and drug relatedness. The event onset will also be shown relative (in number of days) to date of first dose in this study.

Treatment-emergent AEs will be summarized by the number of subjects reporting a TEAE, SOC, preferred term, severity, relationship to study drug (causality), and seriousness. When summarizing AEs by severity and relationship, each subject will be counted only once, within a system organ class or a preferred term, by using the event with the highest severity and greatest relationship within each classification.

Serious AEs will be summarized by severity, and relationship to study drug, and individual SAEs will be listed by subject. In addition, a list of subjects who prematurely discontinue study drug due to an AE, had AEs leading to treatment modification, and AEs that resulted in death will be provided.

Adverse events will also be summarized by windows of duration of exposure to study drug to determine if there is a safety signal due to duration of exposure. The windows of exposure will include but are not limited to: 1) within the first 24 hours (i.e. Day 1 of the LTS study), 2) up to 1 month (i.e. 2-30 days), 3) up to 3 months (i.e. 31-90 days), 4) up to 6 months (i.e. 91-180 days) and 5) up to 12 months (i.e. 181-365 days).

Adverse event incidence will also be summarized by the extent of exposure categories (in grams) as described in section 4.4.

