Treatment Emergent Adverse Events (TEAE) by System Organ Class, Preferred Term, and Duration of Exposure Safety Population

System Organ Class Preferred Term	Within 24 hours (N=XXX)	Within 2-30 days (N=XXX)	Within 31-90 Days (N=XXX)	Within 91-180 Days (N=XXX)	Within 181-365 Days (N=XXX)	Overall (N=XXX)
Number of Subjects with at Least One TEAE Number of Events	xx (xx.x)	xx (xx.x)	xx (xx.x)	xx (xx.x)	xx (xx.x)	xx (xx.x) xx
System Organ Class 1	xx (xx.x)	xx (xx.x)	xx (xx.x)	xx (xx.x)	xx (xx.x)	xx (xx.x)
Preferred Term 1	xx (xx.x)	xx (xx.x)	xx (xx.x)	xx (xx.x)	xx (xx.x)	xx (xx.x)
Preferred Term 2	xx (xx.x)	xx (xx.x)	xx (xx.x)	xx (xx.x)	xx (xx.x)	xx (xx.x)
System Organ Class 2	xx (xx.x)	xx (xx.x)	xx (xx.x)	xx (xx.x)	xx (xx.x)	xx (xx.x)
Preferred Term 1	xx (xx.x)	xx (xx.x)	xx (xx.x)	xx (xx.x)	xx (xx.x)	xx (xx.x)
Preferred Term 2	xx (xx.x)	xx (xx.x)	xx (xx.x)	xx (xx.x)	xx (xx.x)	xx (xx.x)

Note(s): Adverse event terms were coded using MedDRA dictionary version 18.1. Subjects are counted once within each level of summary. Duration of exposure is based on date of first dose of SB204, which could be in the previous study (NI-AC301 or NI-AC302).

Source: Listing xx.x.x.x, Program: xxxxx.sas, Output: T xx.x x x xxxx.rtf, Generated on: DDMMMYYYY HH:MM

Programmer Note: Order SOC by decreasing frequency and preferred term by decreasing frequency within SOC based on overall incidence.

Protocol Number: NI-AC303

Table 14.3.3.2.2

Treatment Emergent Adverse Events (TEAE) by System Organ Class, Preferred Term, and Extent of Exposure Safety Population

System Organ Class Preferred Term	1-100 grams (N=XXX)	>100-330 grams (N=XXX)	>330-675 grams (N=XXX)	>675 Grams (N=XXX)	Overall (N=XXX)
Number of Subjects with at Least One Event	xx (xx.x)	xx (xx.x)	xx (xx.x)	xx (xx.x)	xx (xx.x)
Number of Events	xx	xx	xx	xx	xx
System Organ Class 1 Preferred Term 1 Preferred Term 2	xx (xx.x)	xx (xx.x)	xx (xx.x)	xx (xx.x)	xx (xx.x)
	xx (xx.x)	xx (xx.x)	xx (xx.x)	xx (xx.x)	xx (xx.x)
	xx (xx.x)	xx (xx.x)	xx (xx.x)	xx (xx.x)	xx (xx.x)
System Organ Class 2 Preferred Term 1 Preferred Term 2	xx (xx.x)	xx (xx.x)	xx (xx.x)	xx (xx.x)	xx (xx.x)
	xx (xx.x)	xx (xx.x)	xx (xx.x)	xx (xx.x)	xx (xx.x)
	xx (xx.x)	xx (xx.x)	xx (xx.x)	xx (xx.x)	xx (xx.x)

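### The adverse-event windows by duration of exposure use two incompatible starting points: SAP 4.5.1 ties the first window to LTS Day 1, while SAP 4.4 and the table note count from the first SB204 dose

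*SAP*

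**What the plan says.** **The windows.** SAP 4.5.1 plans to look for a safety signal related to duration of exposure by tabulating events in five windows. The first is "within the first 24 hours (i.e. Day 1 of the LTS study" and the last is "up to 12 months (i.e. 181-365 days". The three between them are 2-30, 31-90 and 91-180 days, with no starting point stated. The list opens with "The windows of exposure will include but are not limited to". Protocol 7.5.1 has the same five windows in terms of exposure to drug. It is likewise open-ended, gives no day ranges, and does not tie the first window to the LTS.

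**The start of exposure.** In SAP 4.4 the "date of first drug administration is the date of first treatment in the previous pivotal study for subjects randomized to SB204". For the others it is the "date of first dose in the LTS for subjects randomized to vehicle in the previous study". The note under shell Table 14.3.3.2.1 agrees: "Duration of exposure is based on date of first dose of SB204, which could be in the previous study (NI-AC301 or NI-AC302".

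**The table.** Shell 14.3.3.2.1 prints the five windows plus Overall. It does not split by prior treatment. Each column has an N, but the shell does not say who is counted in it. Nine further duration tables (14.3.3.3.1 to 14.3.3.11.1) reuse this shell.

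**Which events count.** Under SAP 4.5.1, events are treatment-emergent from the first day of LTS enrolment. Events carried over from the pivotal study are excluded and summarised separately.

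**Timing.** Protocol 3.5 says "Subjects may enter the long term safety study up to 7 calendar days after their Week 12 visit in the pivotal study". Protocol Table 2 sets the final visit at Day 280, plus or minus 7 days. Protocol 3.3 gives 40 weeks as the longest time in the study and makes the pivotal Week 12 visit the Baseline. Protocol 6.2 runs adverse-event reporting to the end of the last visit.

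**The concern.** For SB204 Naive subjects the two starting points coincide, because their first SB204 dose is in the LTS. For Experienced subjects they differ by about 12 weeks. A programmer who follows the SAP text puts an Experienced subject's LTS Day 1 event in window 1. One who follows the table note puts it in a later window. One who takes window 1 from the text and the other windows from the note could count it in both.

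This table is the plan's instrument for detecting an effect of duration, and its content depends on a choice that the SAP makes in two ways. Under the table note, the earliest columns hold only Naive events and the end of the last column holds only Experienced events. A difference between columns would then be mixed with prior treatment, and the shell gives the reader no means of seeing that. The last window also closes at day 365, which is exactly where the nominal schedule ends for Experienced subjects, so it leaves no room for permitted delays.

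**Working it through.** **Inputs.** LTS treatment is 280 days (Protocol 3.4). The entry gap is 0 to 7 days (Protocol 3.5). The final visit tolerance is 7 days either way (Protocol Table 2). Pivotal treatment is 12 weeks (Protocol 3.7.2). Assumption: pivotal Week 12 falls at Day 84. The pivotal visit tolerance is not given. The formula is SAP 4.4's: last date minus first date plus 1.

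**Step 1: reproduce the plan's bound.** Experienced, no gap, final visit on time: 84 + 280 + 1 = 365. This equals the upper limit of the last window, so the windows fit the nominal schedule counted from the first SB204 dose.

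**Step 2: place LTS Day 1 on the exposure scale.** For an Experienced subject with an entry gap of g days it is 84 + g + 1.
- g = 0 gives day 85, and g = 5 gives day 90: the 31-90 day window.
- g = 6 gives day 91, and g = 7 gives day 92: the 91-180 day window.

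Treatment-emergent events start at LTS enrolment, so under the table note an Experienced subject cannot contribute to the Day 1 or 2-30 day columns. Under the SAP text the same subject does contribute to window 1.

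**Step 3: the last possible day for an Experienced subject, from the first SB204 dose.**

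| Situation | Sum | Last day | Days past 365 |
|---|---|---|---|
| Final visit 7 days early | 84 + 280 - 7 + 1 | 358 | 0 |
| Nominal | 84 + 280 + 1 | 365 | 0 |
| 7-day entry gap only | 84 + 7 + 280 + 1 | 372 | 7 |
| Final visit 7 days late only | 84 + 280 + 7 + 1 | 372 | 7 |
| Both | 84 + 7 + 280 + 7 + 1 | 379 | 14 |

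A net delay of one day is enough to pass 365. The tail is 7/287 = 2.4% or 14/287 = 4.9% of LTS follow-up for a subject at the limit, where 287 = 280 + 7. If the pivotal Week 12 visit could itself move by 3 to 7 days either way (assumed), the 379 becomes 372 to 386.

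**Step 4: Naive subjects.** 280 + 1 = 281 on schedule, and 280 + 7 + 1 = 288 at the latest. In the 181-365 day column they can contribute 281 - 180 = 101 to 288 - 180 = 108 days. Experienced subjects can contribute 365 - 180 = 185. After about day 281 to 288 the column is Experienced only.

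**Step 5: the other starting point.** If every window were counted from LTS Day 1, nobody would pass day 288 and no event would lie beyond the last window. The tail in Step 3 exists only under the starting point in SAP 4.4 and the table note.

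**The case against.** The strongest reply concerns the last window. A reader might infer that late events in Experienced subjects are lost from the analysis. The documents do not support that. Shell 14.3.3.2.1 has an Overall column that counts them, and Listing 16.2.8.1 gives the duration of exposure for each event. The window list is expressly not exhaustive, so a further window is already permitted. This reply stands. What remains is that the shell fixes five columns, and they would not account for all of Overall.

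The size of the tail is also open to challenge. Visits are timed from Baseline, and Protocol 3.3 makes the pivotal Week 12 visit the Baseline. On that reading the entry gap is absorbed and the limit is 372, not 379. If the 40-week maximum is strict but counted from LTS entry, the limit is again 372. If that maximum is strict and also counted from pivotal Week 12, the last day is 365 and the tail vanishes, but the 7-day lateness allowed in Protocol Table 2 is then set aside. So 379 is an outer limit.

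A reader might also infer that the 12-month label is wrong because Naive subjects cannot reach it. It is not wrong: the label is an upper bound, and Experienced subjects can reach it. Table 14.2.1 will show duration separately for the two groups, and Table 14.3.3.1 splits the overview of treatment-emergent events by prior treatment. Neither shows who is under observation within each window, so the case for numbers at risk remains.

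None of these replies removes the conflict over the first window.

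**Conclusion.** The conflict of starting points is an error as written. SAP 4.5.1 anchors window 1 at LTS Day 1, whereas SAP 4.4 and the note to Table 14.3.3.2.1 anchor duration at the first SB204 dose. For Experienced subjects the two differ by 84 to 91 days, assuming pivotal Week 12 at Day 84. This decides whether Experienced subjects appear in window 1 at all, and it carries into ten duration-of-exposure tables: the shell and nine repeats.

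The closed last window is a minor edge case that depends on that anchor. It covers no days at nominal timing, 7 days with one permitted delay, and 14 days only if the entry gap and the late final visit add up. The Naive limit of about day 281 to 288 is a fact that the table should disclose. It is not a mistake in the label.

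The number of events affected cannot be estimated from the documents. The matter is minor but cheap to settle.

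**What to change.** 1. In SAP 4.5.1 and all duration-of-exposure shells, count every window from the first SB204 dose as SAP 4.4 defines it, and delete the tie to LTS Day 1 from window 1.
2. Make the last window open-ended (above 180 days), or keep 181-365 and add a window above 365 days, so that the windows cover all of Overall.
3. Print the number at risk in each window by prior treatment (Experienced, Naive), and state that this is the denominator. The reader will then see that the first two columns hold Naive events only and that the last column is Experienced only after about day 281 to 288.

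A further split of the last window at day 288 is optional.

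The cost is a few lines of SAP text and small edits to one shell that the other nine tables reuse. No new data are needed. The choice of anchor and the last window should be fixed before the data are reviewed, so that neither is chosen with the events in view.

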Number of Subjects with Exposure	xx	XX	XX
Mean (SD)	xx.x (xx.xx)	xx.x (xx.xx)	xx.x (xx.xx)
Median	XX.X	XX.X	XX.X
Min, Max	X.X, XX.X	X.X, XX.X	x.x, xx.x
Unknown	,	,	•
Days of Exposure			
n	xx	xx	XX
Mean (SD)	xx.x (xx.xx)	xx.x (xx.xx)	xx.x (xx.xx)
Median	XX.X	XX.X	XX.X
Min, Max	x.x, xx.x	x.x, xx.x	X.X, XX.X
Unknown			
Areas of Application			
Face	xx (xx.x)	xx (xx.x)	xx (xx.x)
Upper Back	xx (xx.x)	xx (xx.x)	xx (xx.x)
Upper Chest	xx (xx.x)	xx (xx.x)	xx (xx.x)
Shoulders	xx (xx.x)	xx (xx.x)	xx (xx.x)
Other	xx (xx.x)	xx (xx.x)	xx (xx.x)
Extent of Exposure (grams)			
Mean (SD)	xx.x (xx.xx)	xx.x (xx.xx)	xx.x (xx.xx)
Median	XX.X	XX.X	XX.X
Min, Max	x.x, xx.x	x.x, xx.x	x.x, xx.x
Unknown	xx (xx.x)	xx (xx.x)	xx (xx.x)
1-100 grams	xx (xx.x)	xx (xx.x)	xx (xx.x)
>100-330 grams	xx (xx.x)	xx (xx.x)	xx (xx.x)
>330-675 grams	xx (xx.x)	xx (xx.x)	xx (xx.x)
>675 grams	xx (xx.x)	xx (xx.x)	xx (xx.x)

Notes: All exposure endpoints includes exposure to SB204 from the previous study (NI-AC301 or NI-AC302), if applicable. Duration of Exposure = Date of Last Drug Administration - Date of First Drug Administration + 1 day. Days of exposure will be defined as the total number of days that the subject reported taking study medication. Areas of application indicate if the subject ever applied drug to that area. Each subject is counted only once per area.

Extent of exposure is determined as: 0.9 grams times the number of application areas times the number of days applied. Application to neck and jawline are considered part of application to the face when determining extent of exposure. Source: Listing xx.x.x.x.x, Program: xxxxx.sas, Output: T xx.x x x xxxx.rtf, Generated on: DDMMMYYYY HH:MM

Protocol Number: NI-AC303

Table 14.2.2.1
Inflammatory Lesion Counts by Study Visit (Face Only)
Safety Population

		SB204 (N=XXX)		
		Count	Absolute Change	Percent Change
Visit	Statistic		from Baseline	from Baseline
Baseline	N	XX		
	Mean	XX.X		
	SD	XX,XX		
	Median	XX		
	Min. to Max.	XX to XX		
Week 4	N	XX	XX	XX
	Mean	XX.X	XX.X	XX.X
	SD	XX, XX	XX,XX	XX,XX
	Median	XX	XX,X	XX,X
	Min. to Max.	XX to XX	XX to XX	XX to XX
Week 12	N	XX	XX	XX
	Mean	XX.X	XX.X	XX.X
	SD	XX,XX	XX,XX	XX,XX
	Median	XX	XX,X	XX,X
	Min. to Max.	XX to XX	XX to XX	XX to XX

Source: Listing xx.x.x.x, Program: xxxxx.sas, Output: T xx.x x x xxxx.rtf, Generated on: DDMMMYYYY HH:MM

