Note(s): Adverse event terms were coded using MedDRA dictionary version 18.1. Subjects are counted once within each level of summary. TEAE onset is based on the start of treatment in the LTS. Extent of exposure is based on first exposure to SB204 - which could be in the previous study (NI-AC301 or NI-AC302).

Source: Listing xx.x.x.x.x, Program: xxxxx.sas, Output: T xx.x x x xxxx.rtf, Generated on: DDMMMYYYY HH:MM

Programmer Note: Order SOC by decreasing frequency and preferred term by decreasing frequency within SOC based on overall incidence.

Protocol Number: NI-AC303

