Previous Study	Subject ID	Drug Class/ Preferred Name/ Reported Term	Indication	Start Date (Day)/ End Date (Day)	Dose (Unit) / Frequency / Route	If for AE or MH, Primary Term	Ongoing from Previous Study?
xxxxxx	xxxxxx	XXXXXXXXXXXXXX/ XXXXXXXXXXXXXX/ XXXXXXXX	Adverse Event	DDMMMYYYY (XX)/ Ongoing			
xxxxxxx	xxxxxxx	XXXXXXXXXXXXX/ XXXXXXXXXXXXXXXXXXXXXXX	Medical History	DDMMMYYYY (XX)/ DDMMMYYYY (XX)	XXX.X (XXXXX) / XXX / XXXXXXXXX	XXXXXXXX	Yes
xxxxxx	xxxxxx	XXXXXXXXXXXX/ XXXXXXXXXXXXX/ XXXXXXXXXX	Prophylaxis	DDMMMYYYY (XX)/ DDMMMYYYY (XX)	XXX.X (XXXXX) / XXX / XXXXXXXXX		
xxxxxxx	xxxxxxx	XXXXXXXXXXXX/ XXXXXXXXXXXX/ XXXXXXXXXX	Dietary Supplement	DDMMMYYYY (XX)/ DDMMMYYYY (XX)	XXX.X (XXXXX) / XXX / XXXXXXXXX	XXXXXXXX	No
xxxxxxx	xxxxxxx	XXXXXXXXXXXX/ XXXXXXXXXXXXX/ XXXXXXXXXX	Contraception	DDMMMYYYY (XX)/ DDMMMYYYY (XX)	XXX.X (XXXXX) / XXX / XXXXXXXXX		
xxxxxxx	xxxxxxx	XXXXXXXXXXXXXX/ XXXXXXXXXXXXXXX/ XXXXXXX	Other: XXXXXXXXXXX	DDMMMYYYY (XX)/ DDMMMYYYY (XX)	XXX.X (XXXXX) / XXX / XXXXXXXXX		

Note(s): Day = Day relative to the first day of LTS. Coding will be done using the WHO March 2016 dictionary. Drug Class corresponds to ACT level 2. s<nnn>xxxx yyyymmddthh:mm

Protocol Number: NI-AC303

Listing 16.2.8.1
Adverse Events
Safety Population

Subject ID	Duration of Exposure (days)	Extent of Exposure (grams)	System Organ Class/ Preferred Term/ Reported Term	T E A E	First Dose Date/ Start Date/ End Date / (Days)	Cause Study Discon- tinuation?	Severity / Relationship	Action / Treatment / Final Outcome	SAE?	SAE Criteria
xxxxxx	xx	xx.x	XXXXXXXXXXXXXXX / XXXXXXXXXXXXX / XXXXXXXX	Y	DDMMMYYY / DDMMMYYYY / DDMMMYYYY / XX	No	Mild / Unlikely	Dose Not Changed / XXXXXXXX / XXXXXXXXXXXXXXX	No	
xxxxxx	XX	XX.X	XXXXXXXXXXXXXX / XXXXXXXXXXXXX / XXXXXXXX	Y	DDMMMYYY / DDMMMYYY / DDMMMYYYY / XX	Yes	XXXXXXX / XXXXXXX	XXXXXXXXX / XXXXXXXXX / XXXXXXXXXXXXXXX	Yes	XXXXXXXXX XX

Note(s): TEAE=Treatment-emergent Adverse Event. TEAE onset is based on the start of treatment in the LTS. Days = (Adverse event end date - event start date)+1. Adverse events were coded using MedDRA 18.1. Duration and extent of exposure are based on the date of first dose of study drug, which could from the previous study (NI-AC301 or NI-AC302). s<nnn>xxxx yyyymmddthh:mm

Protocol Number: NI-AC303

Repeat Listing 16.2.8.1 for:

Listing 16.2.8.2 Treatment-Emergent Adverse Events Leading to Discontinuation of Study Drug Safety Population

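### Sorting adverse events that stop drug by total grams lets the event choose its own column, and no adverse event summary separates treated area from time

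*SAP*

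**What the plan says.** SAP 4.4 says that "extent of exposure (calculated total grams) to study drug will be presented". Each area-day counts 0.9 g, and prior SB204 use in the pivotal study is included. On banding, "extent of exposure will be categorized logically depending on actual distribution of subjects", with quartiles considered first. The Table 14.2.1 shell already prints four bands (1-100, >100-330, >330-675 and >675 g). Its notes say "Extent of exposure is determined as: 0.9 grams times the number of application areas times the number of days applied" and, for the area rows, "Areas of application indicate if the subject ever applied drug to that area".

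SAP 4.5.1 carries these categories to safety: "Adverse event incidence will also be summarized by the extent of exposure categories (in grams) as described in section 4.4". Shell 14.3.3.2.2 uses the same bands as columns, headed for example "1-100 grams (N=XXX)", without defining N. Its note reads "Extent of exposure is based on first exposure to SB204 - which could be in the previous study (NI-AC301 or NI-AC302)". Listing 16.2.8.1 says "Duration and extent of exposure are based on the date of first dose of study drug, which could from the previous study". Both notes fix where counting starts; neither says where it ends. The shell is reused for events leading to discontinuation of study drug (Table 14.3.3.6.2) and for the treatment-related ones (14.3.3.7.2).

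Protocol 7.7 bases extent on treatment days and body surface area (BSA) treated. It wants adverse events summarised by extent to look for a signal from duration or from total body area. SAP 4.5.1 repeats that aim for duration only. Treated area appears in Table 14.2.1 as ever-use and in Listing 16.2.6 by visit.

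**The concern.** There are two separate problems.

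First, on the natural reading the column is the subject's final total. For an event that stops drug, the outcome then limits the variable that classifies it: early stoppers stay in low bands, and the top band fills with people who stayed on drug. The >675 g column could look reassuring about heavy exposure when it shows only who lasted long enough to get there. It could also hide a real rise in risk with area.

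Second, grams multiply area by time, so a pattern across bands cannot be attributed to either. The body-area half of protocol 7.7 is left without an adverse event summary that can answer it.

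**Working it through.** **The SAP's own figures.** 200 × 0.9 = 180 g and (100 + 50) × 0.9 = 135 g, both as in SAP 4.4. Its maximum formula with 84 prior days and 280 study days gives 0.9 × 84 + 0.9 × 4 × 280 = 75.6 + 1008 = 1083.6 g.

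**Who can pass 675 g** (SAP rate of 0.9 g per area-day, 280 days, up to 75.6 g prior):

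- One area: at most 0.9 × (84 + 280) = 327.6 g, so never.
- Two areas: at most 75.6 + 1.8 × 280 = 579.6 g, so never.
- Three areas: more than 675/2.7 = 250 days if naïve, or (675 − 75.6)/2.7 = 222 if experienced.
- Four areas (as the SAP counts them): more than 675/3.6 = 187.5 days, or 599.4/3.6 = 166.5.

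A subject whose event stops drug before about study day 167 cannot be in the top column, whatever the area.

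**Size, by simulation.** The documents give no rates, so these are assumptions: 600 subjects, half experienced; 50/25/25% on one/two/three areas; 30% other dropout by day 280; adverse event hazard 0.5 per year; 10% of events stop drug. Grams = 0.9 × areas × treated days, plus 75.6 if experienced. Percentage of subjects with a discontinuing event:

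| Scenario, printed bands | 1-100 | >100-330 | >330-675 | >675 g |
|---|---|---|---|---|
| No effect | 9.8 | 3.4 | 2.7 | 0.6 |
| Hazard doubles, one to three areas | 11.4 | 4.3 | 4.7 | 1.2 |
| Hazard rises fourfold | 14.9 | 5.9 | 8.4 | 2.3 |

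With no effect the expected counts are about 3.9, 10.8, 3.8 and 0.6 events among 39, 313, 141 and 108 subjects: 19.1 events, or 19.1/600 = 3.2% overall. The top band is lowest or tied in about 89% of simulated trials with no effect and 93% with doubling.

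**Range, no effect, printed bands:**

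- Stopping share 5% or 20%: 5.1/1.8/1.3/0.3 or 17.7/6.8/5.3/1.2.
- Other dropout 15% or 45%: 19.1/3.8/3.0/0.6 or 6.2/3.0/2.4/0.6.
- Area mix 80/10/10 or 20/30/50: 9.8/2.8/2.8/0.6 or 9.7/5.0/3.4/0.6.
- 60% stopping for good in remission within 60 days: 1.0/1.8/2.6/0.6.

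The slope over the lower three bands can therefore vanish or reverse, while >675 g stays lowest. A separate grid of 756 no-effect scenarios (seven area mixes; 0, 50 or 100% experienced; 40-week stopping risk 1, 3 or 10%; other dropout 5 to 40%; 0, 30 or 60% intermittent users) had the printed top band lowest in all 756, at 0.05 to 0.47 of the overall rate.

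**Quartile bands.** In the same grid the top band was below the overall rate in all 756 scenarios (ratio 0.02 to 0.79) but lowest in only 519. With the base-case rates, quartiles give 5.4/1.9/2.5/1.0 with no effect; with an 80/10/10 mix they give 6.7/0.6/1.3/1.8.

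**Does another denominator help?** Same base-case events, no effect, placed by grams at onset:

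- Subjects reaching the band: 0.6/1.9/1.6/0.6%, still not comparable.
- Person-years in band: 0.049/0.050/0.049/0.051 per year, flat as it should be. With doubling: 0.060/0.062/0.086/0.101.

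**Area against time.** 252 g is one area for 252/0.9 = 280 days, or four areas for 252/3.6 = 70 days. Rates per treated year by one/two/three areas recover the simulated truth: 0.05/0.05/0.05 with no effect (9.5/4.8/4.7 events) and 0.05/0.077/0.10 with doubling (9.4/7.2/9.3 events).

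**The case against.** The strongest reply is that the sponsor may mean grams at onset: Listing 16.2.8.1 carries a grams column on each event row, while the subject's total is already in Listing 16.2.6. That reading is open. But for an event that stops drug at onset the two readings give almost the same grams (seven days between onset and last dose adds 0.9 × 7 = 6.3 g per area), and without time at risk as denominator the percentages still do not compare.

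It is also fair that the rates are assumed, the events few, and each discontinuing event listed singly in Listing 16.2.8.2 and traceable to area through Listing 16.2.6. This limits the harm; it does not make the table readable.

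Four stronger readings are tempting but unsupported:

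- *The top band must always read lowest.* This held in every scenario run with the printed bands (in expectation, not in every single trial), but not with quartiles.
- *Every by-grams table slopes down.* In the base case, all events together read 14/27/29/29% with no effect. The modification tables pool reduction, interruption and discontinuation, and their distortion has no fixed direction (rising when most are short interruptions, about flat at one quarter discontinuations, inverse at about half).
- *The SAP has rejected an at-risk denominator.* It leaves N undefined, which is a gap rather than a decision.
- *Protocol 7.7 orders an adverse event table by area.* It asks for a summary by extent, with body area as one purpose. The gram tables respond to the instruction but cannot separate the two components.

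**Conclusion.** The concern holds in a limited form. As written, the two discontinuation tables by grams give a misleading exposure-response display. With the printed bands, >675 g is expected to read lowest with no effect (about 0.6% against 3.2% overall) and still lowest with a true doubling from one to three areas. With quartiles it reads below the overall rate, not necessarily lowest. That the event limits its own column follows from the SAP's arithmetic; the percentages depend on assumed event, dropout and area-mix rates. Treated area is tabulated and listed but never crossed with adverse events, so protocol 7.7's body-area question has no summary that separates area from time.

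The consequence is bounded: about 19 events in the base case, a descriptive study, and overview, severity and overall SAE totals that do not depend on these tables. A reader should not infer that the trial's main safety results are compromised.

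**What to change.** Before database lock:

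1. **Discontinuation tables (14.3.3.6.2, 14.3.3.7.2).** Either drop the by-grams version, or classify by cumulative grams at event onset over treated person-days in each band. State that rule, the meaning of N and the final bands.
2. **Area.** Add to SAP 4.5.1 rates of first TEAE and first TEAE leading to discontinuation per treated person-day, by treated BSA or by area set for the visit interval of onset, overall and by experienced/naïve, with event counts. A bare count of areas is not enough: protocol Table 1 gives 3, 6 and 8% BSA, so one area can mean 3% or 8%. Give rules for Other sites and for intervals set to UNK. Note that area is not randomised and follows the extent of acne, so differences are not causal.
3. **Area count.** Protocol Table 1 combines upper chest and shoulders; SAP Table 1 counts them as two, and the SAP maximum uses four areas. These passages must be reconciled, because the count drives grams and BSA alike.

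The cost is SAP wording, shells and programming. Areas and drug use are already collected at each post-baseline visit, so there is no added subject burden. Downsides: area is known only per visit interval (up to 12 weeks), so changes within an interval are blurred, and discontinuation rates will be imprecise, at roughly 5 to 10 events per area group in the base case.
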